5.4.3.2 Cumulative number of [REDACTED] is calculated as the sum of [REDACTED]

[REDACTED] as compared to the previous scheduled visit are recorded by the [REDACTED] in two distinct categories: [REDACTED] and [REDACTED] at a visit as compared to the previous scheduled visit. The sum of both is the [REDACTED], at that visit compared to the previous scheduled visit. For subjects with missing baseline MRI, the number of [REDACTED] from baseline cannot be assessed and the endpoint is considered missing.

The cumulative number of [REDACTED] is derived as the sum of the [REDACTED] at all scheduled post-baseline MRI visits: [REDACTED] and premature EOT visit if applicable (irrespective if a visit is conducted during PTOP or not), for subjects with only scheduled post-baseline MRI scans.

For subjects with at least one unscheduled post-baseline MRI scan, care needs to be taken in the derivation to avoid double counting of [REDACTED] and the following algorithm applies:

- If a subject has an unscheduled MRI which is the last available MRI in the time period considered: Include that last unscheduled MRI when summing over 'number of new or [REDACTED]' in the same way as the scheduled visits.
- If a subject has an unscheduled MRI which is not the last available MRI for the subject in the time period considered: Do not include that unscheduled MRI. Rationale: New / [REDACTED] at the unscheduled MRI as well as at the later scheduled MRI are reported in reference to the previous scheduled visit. Including both would result in double counting.

To account for varying observation time the analysis will be adjusted by: Time up to the last MRI (years) = Date of last MRI considered in derivation – Randomization date + 1 divided by 365.25 days.

Rationale: The number of [REDACTED] is expected to increase with observation time, not solely by the 'number of [REDACTED]'. Therefore, adjustment by observation time is conducted. As in this study an additional MRI following premature treatment discontinuation is scheduled, the 'number of MRI scans' is not necessarily expected to be a good approximation of the observation time.

Similarly, the cumulative number of [REDACTED] [REDACTED] is derived. All post-baseline MRI visits up to the [REDACTED] visit (or if missing [REDACTED]) are considered.

Cumulative number of [REDACTED]
Cumulative number of [REDACTED] on treatment is derived in the same way as above but only considering MRI scans recorded between study treatment start and [REDACTED]. The time up to last MRI scans included in the derivation of the variable is calculated and used for adjustment in the analysis.

5.4.3.3 Cumulative number of [REDACTED]
Derived in the same way as for [REDACTED] [REDACTED] [see Section 5.4.2.2], but only including MRI scans up to the [REDACTED] (if missing, up to [REDACTED])

Note that if an unscheduled MRI becomes the last available MRI in the considered time period it is to be included in deriving the sum of lesions.

5.4.3.4 Percent Change of [REDACTED]
[REDACTED]

Percent change of [REDACTED] [REDACTED] is not manually derived, but taken directly from the [REDACTED] at the corresponding scheduled [REDACTED] visit (irrespective if during PTOP or not). Percent change from baseline to [REDACTED] is defined in a similar way.

Handling of missing MRI results follows the general rules for MRI data described in Section 5.4.3 above, with [REDACTED] and [REDACTED] LOCF variables also derived.

Variables for supplementary analysis

For analysis using a repeated measurements model all post-baseline MRI scans will be included ([REDACTED] [REDACTED] [REDACTED]) with time (days from randomization to each MRI scan) as continuous covariate. Percent change of [REDACTED] from baseline will be taken from the corresponding central reader variable, and the time up to each MRI scan (in days) from randomization is derived as Date of MRI scan – Date of randomization + 1.

5.4.3.5 Change from baseline in the [REDACTED] [REDACTED] and to [REDACTED]

[REDACTED] is recorded by the central reader at each visit ([REDACTED]).

Change from baseline in the [REDACTED] at a visit is calculated as the value at a post-baseline visit minus the value at Baseline visit. It is derived for [REDACTED] and [REDACTED] from the corresponding visit (irrespective if conducted during PTOP or not).

Handling of missing MRI results follows the general rules for MRI data described in Section 5.4.3 above, with [REDACTED] LOCF and [REDACTED] LOCF variables also derived.

5.4.3.6 Change from baseline in the [REDACTED] to [REDACTED] and [REDACTED]

[REDACTED]

Handling of missing MRI results follows the general rules for MRI data described in Section 5.4.3 above, with [REDACTED] [REDACTED] and [REDACTED] [REDACTED] variables also derived.

5.4.3.7 Absence of [REDACTED] [REDACTED] and [REDACTED]

[REDACTED] at [REDACTED] and [REDACTED] are considered ‘absent’, if the number of [REDACTED] at [REDACTED] and at [REDACTED] is zero. If > 0 they are considered ‘present’.

See Section 5.4.3.1 for derivation of ‘[REDACTED] at [REDACTED] and [REDACTED] at [REDACTED]’. If no MRI result at the visit is available, the information is considered missing.

Similarly, ‘[REDACTED] to [REDACTED] (including all unscheduled scans)’ (required for derivation of [REDACTED] in Sections 5.4.4.4– 5.4.4.5) is defined ‘absent’ if the ‘number of new Gd+ T1 lesions’ at all post-baseline [REDACTED] up to the [REDACTED] MRI visit (if missing, up to EOS) is zero. This includes all scheduled and all unscheduled visits. If > 0 at any visit it is considered ‘present’. The corresponding ‘Number of MRI scans’ and time to last MRI scan is derived. If no MRI result at the visit

is available (based on visit window), the information is considered missing (for lesion free subjects).

5.4.3.8 Absence of [REDACTED] at [REDACTED] and [REDACTED]
[REDACTED] as compared to baseline are considered 'absent', if the number of [REDACTED] is zero at all scheduled and unscheduled visits up to [REDACTED]. If it is > 0 at any visit it is considered 'present'.

[REDACTED] at [REDACTED] as compared to baseline are considered 'absent', if the number of [REDACTED] is zero at all scheduled and unscheduled visit up to [REDACTED] (or if the [REDACTED] visit is missing but the subject has absence of lesions up to [REDACTED]. If it is > 0 at any visit up to [REDACTED] (or if the [REDACTED] visit is missing up to [REDACTED] it is considered 'present'.

If no MRI result at the respective visit is available (based on visit window) or no baseline MRI is available, the information is considered missing (for lesion free subjects).

5.4.3.9 Proportion of [REDACTED]

Only defined for subjects with [REDACTED] present at baseline.

It is the proportion (%) of [REDACTED]. Results from the [REDACTED] visit are considered irrespectively if conducted during PTOP or not. In addition, it is derived at the [REDACTED] visit. Number of [REDACTED] by visit (at [REDACTED] and at [REDACTED] is considered as separate variable.

The number of [REDACTED] by visit is taken from the central reader (variable [REDACTED]). For [REDACTED], [see Section 5.4.3.1].

Handling of missing MRI results follows the general rules for MRI data described in Section 5.4.3 above. In addition, a variable with LOCF imputation at [REDACTED] and [REDACTED] is derived. For subjects with missing results (either at baseline or post-baseline), the proportion is considered missing.

5.4.4 Other clinical efficacy variables

5.4.4.1 Time to [REDACTED]

The time to first confirmed relapse (in days) is defined as [Date of [REDACTED] – Date of randomization + 1] in days.

Subjects without any [REDACTED] will be censored at the EOS date, and the time is defined as [Date of EOS – Date of randomization + 1] in days.

Derivation of [REDACTED] from randomization up to EOS is detailed in Section 5.4.1. Among these [REDACTED], the earliest [REDACTED] start date is the 'Date of [REDACTED]'. For analysis the variable is displayed in weeks: variables in days divided by 7.

5.4.4.2 Absence of [REDACTED] to [REDACTED] and [REDACTED]
For the derivation of this variable [REDACTED] and their corresponding onset dates, as defined in Section 5.4.1, are considered.

Absence of [REDACTED] to [REDACTED] outcomes are derived as:

'Yes' at [REDACTED] Subjects are considered not [REDACTED] at [REDACTED] if any confirmed [REDACTED] starting between randomization date and [REDACTED] is recorded.

'No' at [REDACTED] Subjects are considered [REDACTED] at [REDACTED] if no [REDACTED] starting between randomization date and [REDACTED] is recorded, and they were still on study on [REDACTED] (EOS date on or after [REDACTED]).

'Missing' at [REDACTED] Subjects without [REDACTED], but no longer on study on Day 420, are considered missing.

Absence of [REDACTED] from baseline to EOS ([REDACTED]) is derived in the same way as above but replacing [REDACTED] with EOS day. Relapse free subjects with premature study withdrawal prior to [REDACTED] ([REDACTED]) will be considered to have 'Missing' outcome.

5.4.4.3 Change in [REDACTED] to [REDACTED]

Absolute changes [REDACTED] by visit are derived, based on the overall [REDACTED] as reported by the investigator in the eCRF [see Section 5.4.2.3.1]. For subjects prematurely discontinuing treatment, results collected during PTOP are considered at the corresponding nominal visit in the same way as for subjects completing treatment at [REDACTED] as planned (e.g. by visit analysis at [REDACTED] considers both [REDACTED] and 'PTOP [REDACTED] visits). Baseline [REDACTED] is defined as in Section 5.4.2.3.1.

On-treatment [REDACTED] will be flagged, i.e., [REDACTED] performed after study treatment start (date/time) and prior to EOT + 7 days.

5.4.4.4 [REDACTED]

[REDACTED]. If at least one of the criteria is not fulfilled or the subject discontinues treatment prematurely, the subject is not considered to have achieved [REDACTED].

Derivation details

A subject is considered as having [REDACTED] activity if at least one of the following applies:

- [REDACTED] derived as detailed in Section 5.4.1.
- [REDACTED] present [see Section 5.4.3.7].
- [REDACTED] o [REDACTED] present [see Section 5.4.3.8].
- [REDACTED]; see Section 5.4.2.3.1 for event derivation and event date.

Subjects that discontinue treatment prematurely are considered as showing [REDACTED], irrespective of what the reason for treatment discontinuation is.

Subjects [REDACTED] as defined above, who have missing outcome for any component (absence of [REDACTED] ([REDACTED] a [REDACTED]) are considered to have missing outcome for [REDACTED] to [REDACTED]

Derived in same way as above but replacing always EOS (or [REDACTED] with [REDACTED] Subjects that discontinue treatment prematurely but after [REDACTED] ([REDACTED]) are considered to have achieved [REDACTED] at [REDACTED] unless any other condition is met. Subjects [REDACTED] with missing outcome for any component at [REDACTED] are considered missing.

5.4.4.5 [REDACTED]

No [REDACTED] is defined by the [REDACTED] [REDACTED] If at least one of the criteria is not fulfilled or the subject discontinues treatment prematurely, the subject is not considered to have achieved [REDACTED]

Derivation is as for [REDACTED], but in addition a subject is considered as having [REDACTED] [REDACTED] if the following applies:

- [REDACTED] [REDACTED] [see Section 5.4.3.4].

[REDACTED] [REDACTED]

Derived in same way as above but replacing always EOS (or [REDACTED] with [REDACTED] Subjects who discontinue treatment prematurely but after [REDACTED] [REDACTED] are

considered to have achieved [REDACTED] at [REDACTED] unless any other condition is met. Threshold for percent change of brain volume at [REDACTED] is $\leq -0.4\%$.

5.4.4.6 *Change in* [REDACTED]

The [REDACTED]

[REDACTED] will be assessed at pre-randomization [REDACTED] and at [REDACTED] and at unscheduled visits due to [REDACTED] or other unscheduled visits ([REDACTED] etc.) and if applicable, at the corresponding visits in the PTOP. The outcome is recorded in the eCRF.

For each assessment, the [REDACTED] score will be calculated as the mean of the Z-scores of the [REDACTED]

[REDACTED]

Details for generating the [REDACTED] Z-score and how to handle missing data are given in Appendix C.1.

For analysis, baseline and nominal post-baseline visits are considered. See Section 11.3 for remapping of premature end of treatment or unscheduled visits (includes unscheduled visits due to relapse).

Baseline is defined as the last available [REDACTED] score prior to or on randomization date. While this should usually present the subjects [REDACTED] the [REDACTED] may be used. A flag is added indicating the [REDACTED] conducted up to the [REDACTED] inclusive.

Furthermore, to address premature study discontinuation an additional variable based on last observation carried forward (LOCF) is derived.

5.4.4.7 Change in the [REDACTED]

The [REDACTED]
[REDACTED] It is administered along with the [REDACTED] at pre-randomization (3 tests, where the first 2 are considered practice tests) and at [REDACTED], [REDACTED], and if applicable, at the corresponding visits in the PTOP and at unscheduled visits (due to [REDACTED] or other unscheduled visits) and its outcome the [REDACTED] score is recorded in the eCRF.

For analysis, baseline and nominal post-baseline visits are considered. See Section 11.3 for remapping of premature end of treatment or unscheduled visits.

Baseline is defined as the last available [REDACTED] score prior to or on randomization date. While this should usually present the subjects [REDACTED] A flag is added indicating the [REDACTED] conducted up to the [REDACTED].

Furthermore, in order to address premature study discontinuation an additional variable based on last observation carried forward (LOCF) is derived.

5.4.4.8 [REDACTED]

[REDACTED] as a binary variable and defined as:

- [REDACTED] the threshold has been derived based on a blinded interim analysis anchored on the [REDACTED]

5.4.4.9 Change from baseline by visit up to [REDACTED]

The [REDACTED]

[REDACTED]

For each of these [REDACTED] (higher score implies greater [REDACTED]) are calculated from the scores of the items in the

respective sub-domains. A total score will not be computed for the [REDACTED] as the research interest, currently, is on the [REDACTED]. See Appendix C.3 for details on the scoring.

It is derived for the following time points: Baseline, [REDACTED]
[REDACTED] [REDACTED] Change from baseline is defined as absolute change from baseline.

5.4.4.10 Change from baseline in [REDACTED]

The [REDACTED]

[REDACTED] The questionnaire will be administered in an electronic format.

PGI-S of Fatigue is completed during the pre-randomization period at [REDACTED] and at unscheduled visits (due to [REDACTED] or other unscheduled visits). If applicable, [REDACTED] will also be performed at the corresponding visits in the PTOp. For analysis, visits are assigned based time windowing as detailed in Section 11.3.

Absolute change from baseline is derived with baseline defined as last available score up to and including randomization date.

5.4.4.11 Change from baseline in [REDACTED]

The [REDACTED]

[REDACTED] The questionnaire will be completed on a paper form and subsequently transcribed in the eCRF.

[REDACTED] will be completed at [REDACTED] and at unscheduled visits (due to [REDACTED] or other unscheduled visits). If applicable, CGI-C will also be performed at the corresponding visits in the PTOp. For analysis, nominal visits are considered. See Section 11.3 for remapping of premature end of treatment or unscheduled visits.

5.5 Safety variables

5.5.1 Definition of treatment-emergency, baseline and change-from-baseline, last on treatment, follow-up assessments for safety variables

For all safety data analyses described in this SAP, baseline is considered to be the last valid assessment prior to first study drug intake.

For each individual safety variable, baseline is defined to be the last valid measurement available before the date and time of first dose intake of study treatment, unless otherwise specified. On days where study drug is initiated or re-initiated, the pre-dose assessment for that day is defined as the last non-missing assessment prior to the study drug intake on that day. The pre-dose assessment on Day 1 (if available) is identical to baseline; however, missing pre-dose data on Day 1 is not imputed with baseline. In case of (partially) missing assessment dates/times, or for assessments reported on Day 1 (or day of re-initiation) with recorded assessment time contradicting the time point label (e.g., pre-dose, 2 hours post-dose), the nominal visit and time point labels will be used to determine whether an assessment is considered for baseline (for example a blood pressure measurement with an assessment date on Day 1 but with a missing assessment time or an assessment time prior to the reported time of first study drug intake, will not be considered for baseline if reported under the time-point “2 hours post-dose” in the eCRF, however it will be considered if reported as “Pre-dose” in the eCRF).

Absolute changes from baseline are defined as post-baseline value minus baseline value, i.e., a positive sign indicates an increase compared to baseline.

A percentage change from baseline is defined as the absolute change from baseline divided by the baseline value (if the baseline value is > 0) and then multiplied by 100.

Absolute and percent change from baseline is calculated and stored for all continuous safety data.

In addition, the following assessments are flagged or derived per parameter:

- Last on-treatment assessment: Last assessment prior to or on EOT date +1 day)
- Day-15 follow-up, between EOT + 8 days and EOT + 22 days [see Section 11.4]
- Day-30 follow-up, between EOT + 23 days and EOT + 37 days [see Section 11.4]
- Last follow-up assessment: Last assessment between EOT + 8 and EOT + 37 days

A safety assessment (ECG, vital signs, laboratory) is considered treatment-emergent, if the assessment date is on or after the study treatment start date and prior to or on the study treatment end date + 15 days (inclusive). If both, the assessment date/time and the date/time of study treatment start are available, only events with date/time on or after the date/time of study treatment start are considered to be treatment emergent. In case of (partially) missing assessment dates/times, or for assessments on treatment Day 1 with reported assessment time contradicting the time point label, the nominal visit and time point labels will be used to determine whether an assessment is considered as treatment-emergent or not. For example, a blood pressure measurement with an assessment date on Day 1 but a missing assessment time or an assessment time after the time of first study drug intake, will not be considered treatment emergent if reported under the time-point “Pre-dose” in the eCRF, however it will be considered if reported as “2 hours post-dose” in the eCRF.

A safety event (AE, SAE, Death) is considered treatment-emergent if the onset date/date of occurrence is on or after the study treatment start date and prior to or on the EOT date + 15 days (inclusive). Missing or partially missing onset or occurrence dates are imputed as described in Section 12.3. If both the onset/occurrence date/time and the date/time of study treatment start are available, only events with date/time on or after the date/time of study treatment start are considered to be treatment emergent.

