2.1.1 Periods

The study consists of the following protocol defined periods:

- **Pre-randomization period** starts with signature of the Informed Consent Form (ICF) and ends with subject's randomization and lasts up to 45 days (per screening attempt). Subjects can be re-screened once.
- **Treatment period** starts on the day of randomization immediately after the 1st dose of study drug intake (Visit 3–Day 1 of the study) and continues until the premature discontinuation of study drug or the scheduled End-of-Treatment (EOT) visit at Week 108. Subjects receive double-blind treatment throughout the treatment period. The treatment period consists of a titration and a maintenance phase.
 - A 2-week titration scheme is implemented on Day 1 (or at re-initiation following a treatment interruption of more than 3 days) to reduce the first-dose effect of ponesimod [see [Table 1](#)].
 - The titration phase is followed by the maintenance phase with one capsule of ponesimod 20 mg or teriflunomide 14 mg administered orally once daily in the morning (from Day 15 to End-of-Treatment [EOT]).

- **Post-treatment period** starts immediately after the last dose of study drug and ends with the End-of-Study visit. It comprises the post-treatment safety follow-up (FU) period and if applicable, the PTOp. During the post-treatment period, all subjects undergo the accelerated elimination procedure of teriflunomide lasting for 11 days with administration of cholestyramine (8 mg three times daily, or if not tolerated 4 mg three times daily) or activated charcoal (50 g two times daily), see protocol for details.
 - **Post-treatment safety follow-up period**
For subjects who enter the extension study AC-058B303, the safety FU period ends with the FU1 visit (scheduled 14–22 days after last dose of study drug). If they have not complied with the teriflunomide accelerated elimination procedure at the time of FU1, it ends with the abbreviated FU2 visit (scheduled 23–37 days after the last dose of study drug).

For subjects who do not enter the extension study, the safety FU period ends with FU2 visit (scheduled 30–37 days after last dose of study drug).
 - **Post-treatment observation period**

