11.3 Re-assignment of premature EOT visits / Visit windowing

For all parameters unless stated below: For subjects who discontinued study drug prematurely with available premature EOT visit, the visit may be re-assigned to a scheduled visit as follows:

- If a result is missing for a scheduled visit, it can be replaced with a result from a premature EOT visit available in the respective visit window [see [Table 9](#)].

Table 9 Premature end of treatment remapping

Visit window	Nominal value Day	Lower limit for Day	Upper limit for Day
Week 2	15	2	22
Week 4	29	23	70
Week 12	85	71	126
Week 24	169	127	210
Week 36	253	211	294
Week 48	337	295	378
Week 60	421	379	462
Week 72	505	463	546
Week 84	589	547	630
Week 96	673	631	714
Week 108	757	715	Open end

Day refers to treatment day, i.e., days from study treatment start.

MRI: For MRI measurements visit windowing of premature EOT visits is conducted using ± 3 months around the target day (Week 60: Day 330 to Day 512; Week 108: \geq Day 665) to account for the less frequent assessment schedule.

Patient reported outcomes collected on electronic device: For patient reported outcome data collected via an electronic device visit windowing is applied as a general process. Rationale is that incorrect visit labels are not corrected via a query process whereas the questionnaire date is tracked automatically by the device therefore, the latter is considered to provide most reliable information. Questionnaires based on dates will be assigned to the visits based on [Table 10](#). If multiple questionnaires are available, the one closest to target is selected.

Physician reported questionnaire and other composite assessment data [REDACTED] [REDACTED] Nominal visits are considered. If missing at the nominal visit, data from a premature end of treatment visit (if not available or appropriate then from an unscheduled visit) is assigned to the visits based on [Table 10](#). If multiple unscheduled assessments qualify the one closest to target is selected.

Table 10 Visit windowing for questionnaire and psychometric assessment data

Visit window	Nominal value Day	Lower limit for Day (Week)	Upper limit for Day (Week)
Baseline	-1	Open end	1
Week 12	85	2 (W0+)	126 (W18)
Week 24	169	127 (W18 ⁺)	294 (W42)
Week 60	421	295 (W42 ⁺)	504 (W72)
Week 84	589	505 (W72 ⁺)	672 (W96)
Week 108	757	673 (W96 ⁺)	Open end

Day refers to study day, i.e., days from randomization date. Wx+ = after week x.

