2.7. Other

Condition	Type	Identifier	Source/Instructions	Additional information expected?	Important PD
Any protocol scheduled visit not done (except follow-up and EOT visits)	M	PD_MM.178	eCRF / Monitor PD		No
Study drug administered but randomization not done per IRT system	M	PD_MM.119	eCRF / Monitor PD		Yes
Study drug administered but date/time of first dose < date/time of randomization	P	PD_PP.048	eCRF		Yes
Any pre-dose assessment performed post-dose (except pre-dose PK sampling)	M	PD_MM.129	eCRF / Monitor PD/ For CDDM only: to be coded once per visit if all assessments done post-dose		No
Any randomized subject who never received study drug	M	PD_MM.175	eCRF / Monitor PD		No
Any pre-dose PK sampling performed post-dose	M	PD_MM.158	eCRF / Monitor PD		No
Any PK sample not taken	M	PD_MM.193	eCRF / Monitor PD		No
Missing information in source documents related to treatment period	M	PD_MM.137	Monitor PD / e.g., assessment time		No
Vaccine-specific antibody titers assessment before and/or after non-live vaccination not performed	M	PD_MM.128	eCRF / Monitor PD		No
Any scheduled visit performed out of time-window (except EOT and follow-up visits)	P	PD_PP.182	eCRF/ For CDDM only: to be added manually in case of Day 15 or first post re-initiation visit out of time-window; to be inactivated manually when present on Visit 14		No

3. After End of Treatment

	TPL-100062 Protocol Deviation Code List
Protocol Number: AC-058B301 Acronym: OPTIMUM	

Note: Applies any time after end of treatment unless specified otherwise, (e.g., during PTOP)

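### SAP 5.5.1 lets the time-point label override the recorded time on Day 1 without excepting 'Pre-dose' readings confirmed as taken after dosing, so such a reading can become baseline and leave the treatment-emergent results

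*SAP*

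**What the plan says.** SAP 5.5.1 states the principle twice. For all safety analyses "baseline is considered to be the last valid assessment prior to first study drug intake", and for each variable "baseline is defined to be the last valid measurement available before the date and time of first dose intake of study treatment", unless specified otherwise. It adds: "The pre-dose assessment on Day 1 (if available) is identical to baseline".

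The section then turns to doubtful times. Its rule covers Day 1 and any date on which treatment is re-initiated. For an assessment there "with recorded assessment time contradicting the time point label (e.g., pre-dose, 2 hours post-dose), the nominal visit and time point labels will be used". This settles whether the value may serve as baseline. The parallel rule for treatment-emergent status covers Day 1 and has a worked example: a blood pressure reading with "an assessment time after the time of first study drug intake, will not be considered treatment emergent if reported under the time-point" 'Pre-dose'.

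The protocol deviation code list attached to the SAP (section 2.7, Other) includes PD_MM.129: "Any pre-dose assessment performed post-dose (except pre-dose PK sampling". Its sources are the eCRF and monitor reports. Section 5.5.1 does not refer to it.

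**The concern.** A label rule is reasonable when nobody knows which of two entries is wrong. It is not reasonable once the late timing has been confirmed. The time is then right and the label wrong, yet 5.5.1 still follows the label.

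The SAP says that titration is used "to reduce the first-dose effect of ponesimod" (section 2.1.1). A 'Pre-dose' ECG or blood pressure reading that was really taken after the dose may already contain part of that effect. Used as the reference, it shrinks every hourly change from pre-dose for that subject. Because the Day 1 pre-dose value is also the baseline, it shifts later changes from baseline too. The relative flags in 5.5.10.1 and 5.5.11.1 depend on the same reference: PR above 200 ms with a rise above 20 ms, QTc increases above 30 or 60 ms, SBP falls of at least 20 mmHg and DBP falls of at least 15 mmHg. The late reading itself also drops out of the treatment-emergent outlier counts.

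**Working it through.** The SAP gives no figure to reproduce. The check is a reading of the rules against each other, followed by an illustration with assumed values.

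**1. What the rules do with a 'Pre-dose' reading timed after first intake**

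- *Definition of baseline (5.5.1):* the reading does not qualify, because it does not precede the dose.
- *Label rule for baseline (5.5.1):* the reading qualifies. This follows from the general sentence. The example given there covers only a missing time or a time before first intake.
- *Treatment-emergent status (5.5.1):* where both date/times are available, only those on or after treatment start count, so the reading would be in. The label rule then takes it out, this time by explicit example.
- *Deviation list (PD_MM.129):* the situation is foreseen and can be confirmed.
- *Exception for confirmed cases:* none is stated.

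For a confirmed late reading, the label rule and the definition of baseline therefore give opposite answers.

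**2. What is not touched**

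- Adverse events are classified by actual onset date and time (5.5.1).
- Correctly labelled post-dose readings, taken hourly for at least 4 h (schedule notes, section 2.2), stay treatment-emergent. Absolute flags at those hours, such as heart rate at or below 40 bpm, are unchanged.

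**3. Effect on an arm mean (assumed inputs)**

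Let f be the share of ponesimod subjects whose 'Pre-dose' value was really post-dose, and E the first-dose change already present in it. Neither is in the SAP. The mean change from pre-dose is understated by f × E:

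- 0.01 × 2 bpm = 0.02 bpm
- 0.05 × 5 bpm = 0.25 bpm
- 0.10 × 10 bpm = 1.0 bpm

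**4. Effect in one subject (assumed values)**

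True pre-dose PR is 180 ms, the late 'Pre-dose' ECG shows 190 ms, and a later reading shows 205 ms.

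- Against the true value: 205 − 180 = 25 ms, and 205 > 200, so the reading is flagged.
- Against the late value: 205 − 190 = 15 ms, so it is not flagged.

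For an affected subject the whole of E is lost from each change from pre-dose.

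**The case against.** The other side has a good deal to say, and most of it stands.

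- **A conflict is not proof of a late reading.** Either entry may be wrong, and the dose time is itself a reported eCRF entry. If the time is the error, the label gives the right answer. A reader might infer that 5.5.1 admits known post-dose readings whenever time and label disagree, or that the clock should always win. The text supports neither. Clock-first would turn true pre-dose readings with mistyped times into treatment-emergent values.
- **PD_MM.129 shows no occurrence.** A code list names possible deviations. This code is not limited to Day 1, ECG or blood pressure, and it is not classed as important.
- **Section 11.3 is no contradiction.** For electronic questionnaires the SAP does prefer the device, "whereas the questionnaire date is tracked automatically by the device therefore, the latter is considered to provide most reliable information". It does so because incorrect visit labels in those data are not corrected by query, and nothing extends that reason to Day 1 time-point labels.
- **The ECG sections follow nominal time.** Section 5.5.11.1 uses date-time only to choose among duplicates within a nominal time point. Section 9.10.3 takes 3-hour ECGs as reported, whatever their actual time.
- **The baseline definition allows exceptions.** One of its two statements ends with a rider, so the label rule could be read as a permitted exception.

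The last point does not rescue the confirmed case. The label rule is a way to decide whether a reading preceded the dose when that is in doubt. After confirmation no doubt is left, and the rule should give way.

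**Conclusion.** The point holds in a narrow form. Section 5.5.1 has no exception for 'Pre-dose' readings confirmed as taken after dosing. For those readings it yields a baseline and an emergent status that conflict with its own definition of baseline.

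It would go too far to say that the rule hides the first-dose effect. Attenuation is possible but not shown: the SAP gives neither the number of affected records nor the size of the effect. The rule is the same in both arms, so a one-sided distortion rests on the assumption that the first-dose effect is specific to ponesimod. The effect on arm means is probably small (0.02 to 1.0 bpm under the assumed ranges). The relative flags and changes of individual affected subjects matter more. The change is still worth making, because it costs little and concerns the analyses meant to describe the first dose.

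**What to change.** In 5.5.1, keep the label rule for missing times and for conflicts that remain unresolved. Add an exception for confirmed late readings: PD_MM.129, with the affected record identified by its recorded time against the recorded dose time, or by the ECG machine time stamp. For these records:

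- do not use the value as baseline or pre-dose;
- take baseline from the last assessment before dosing;
- set the Day 1 pre-dose value to missing, in line with the existing rule that it is not filled in from baseline;
- count the record as treatment-emergent.

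Add a sensitivity summary of Day 1 ECG and blood pressure by actual time.

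The cost is a short text change, some derivation code and one extra summary. A few subjects lose their pre-dose value from the by-hour change tables. The work must be done record by record: PD_MM.129 may be coded once for a whole visit, and the list asks for no additional information with it, so the code alone may not identify the parameter affected.
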